12.5 Analysis of secondary endpoints/estimands

12.5.1 Efficacy and/or Pharmacodynamic endpoint(s)

The secondary efficacy variables are described below. Secondary efficacy variables will be analyzed using the FAS population. Handling of missing data for secondary variables will be the same as for the primary variable.

ACR50 at Week 16

Response at Week 16 to ACR50 in the FAS will be evaluated using a logistic regression model with treatment group as a factor and weight as a covariate.

DAS28-CRP at Week 16

Between-treatment differences in the change from BSL in DAS28-CRP will be evaluated using MMRM with treatment group and analysis visit as factors and BSL DAS28-CRP score and weight as continuous covariates. Treatment by analysis visit and BSL DAS28-CRP score by analysis visit will be included as interaction terms in the model. An unstructured covariance structure will be assumed for the model.

PASDAS at Week 16

Between-treatment differences in the change from BSL in PASDAS will be evaluated using MMRM with treatment group and analysis visit as factors and BSL PASDAS score and weight as continuous covariates. Treatment by analysis visit and BSL PASDAS score by analysis visit will be included as interaction terms in the model. An unstructured covariance structure will be assumed for the model.

SF-36 PCS at Week 16

See Section 12.5.7 PROs.

Physical function (HAQ-DI[©]) at Week 16

Between-treatment differences in the change from BSL in HAQ-DI[©] will be evaluated using MMRM with treatment group and analysis visit as factors and BSL HAQ-DI[©] score and weight as continuous covariates. Treatment by analysis visit and BSL HAQ-DI[©] score by analysis visit will be included as interaction terms in the model. An unstructured covariance structure will be assumed for the model.

12.5.2 Safety endpoints

Adverse events

Treatment-emergent adverse events (i.e., events started after the first dose of study treatment or events present prior to the first dose of study treatment but increased in severity based on preferred term and on or before last dose + 84 days) will be summarized.

Adverse events will be summarized by presenting, for each treatment group, the number and percentage of participants having any AE, having an AE in each primary system organ class and having each individual AE (preferred term). Summaries will also be presented for AEs by severity and for study treatment related AEs. If a participant reported more than one adverse event with the same preferred term, the adverse event with the greatest severity will be presented. If a participant reported more than one adverse event within the same primary system organ class, the participant will be counted only once with the greatest severity at the system organ class level, where applicable. Serious adverse events will also be summarized.

These summaries may be presented separately by study periods.

As appropriate, the incidence of AEs will be presented per 100 patient years of exposure (exposure-adjusted incidence rates).

Separate summaries will be provided for death, serious adverse event, other significant adverse events leading to discontinuation and adverse events leading to dose adjustment (including study treatment discontinuation).

A graphical display of relative frequencies within system organ classes and relative risks, as appropriate, will be presented.

When adjudication is required of major cardiovascular events, a summary of those types of events as reported by the investigator and confirmed by adjudication will be provided.

Laboratory data

The summary of laboratory evaluations will be presented for three groups of laboratory tests (hematology and serum chemistry). Descriptive summary statistics for the change from BSL to each study visit will be presented. These descriptive summaries will be presented by test group, laboratory test and treatment group. Change from BSL will only be summarized for participants with both BSL and post BSL.

For each parameter, the maximum change from BSL within each study period will be evaluated analogously.

In addition, shift tables will be provided for all parameters to compare a participant's BSL laboratory evaluation relative to the visit's observed value. For the shift tables, the normal laboratory ranges will be used to evaluate whether a particular laboratory test value was normal, low, or high for each visit value relative to whether or not the BSL value was normal, low, or high. These summaries will be presented by laboratory test and treatment group. Shifts will be presented by visit as well as for most extreme values post-BSL.

Vital signs

Analysis of the vital sign measurements using summary statistics for the change from BSL for each post-BSL visit will be performed. These descriptive summaries will be presented by vital sign and treatment group. Change from BSL will only be summarized for participants with both BSL and post-BSL values.

ECG

Summary statistics will be presented for ECG variables by visit and treatment group. Qualitative changes will be summarized.

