| Start of the clinical trial | The start of the clinical trial is defined as the signature of the informed consent by the first participant |
| Study treatment | Any drug or combination of drugs or intervention administered to the study participants as part of the required study procedures; includes investigational drug(s), control(s) or background therapy |
| Study treatment discontinuation | When the participant permanently stops taking any of the study drug(s) prior to the defined study treatment completion date (if any) for any reason; may or may not also be the point/time of study discontinuation |
| Treatment arm/group | A treatment arm/group defines the dose and regimen or the combination, and may consist of 1 or more cohorts. |
| Variable (or endpoint) | The variable (or endpoint) to be obtained for each participant that is required to address the clinical question. The specification of the variable might include whether the participant experiences an intercurrent event. |
| Withdrawal of consent (WoC) | Withdrawal of consent from the study occurs only when a participant does not want to participate in the study any longer and does not allow any further collection of personal data |

Protocol summary

| FIOLOCOI SU | |
|-------------------------------|---|
| Protocol number | CAIN457F2367 |
| Full Title | A phase III randomized, double-blind, placebo controlled, multicenter, bridging study of subcutaneous secukinumab, to demonstrate efficacy after sixteen weeks of treatment and to assess safety, tolerability and long-term efficacy follow-up to one year in Chinese subjects with active psoriatic arthritis |
| Brief title | Study of efficacy and safety of secukinumab in Chinese subjects with active PsA compared to placebo |
| Sponsor and Clinical Phase | Novartis Phase III |
| Investigation type | Biological |
| Study type | Interventional |
| Purpose and rationale | The purpose of this bridging study is to assess the efficacy and safety of secukinumab 150 mg subcutaneous (s.c.) in Chinese participants with active PsA compared to placebo to support registration in China. |

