4.1 Rationale for study design

| Study Design Aspect | Rationale |
|--|--|
| Overall (double-blind, randomized, parallel-group, placebo-controlled) | The double-blind, randomized, parallel-group, placebo-controlled design used in this study up to Week 16 is in alignment with Phase III trials of other biologics in this disease area and in compliance with the European Medicines (Evaluation) Agency (EMA/EMEA) guidelines (EMA 2006) and China Food and Drug Administration (CFDA) requirement in use of biologics drug. The design in this study up to Week 16 is similar with global PsA Phase III trials, to enable the evaluation of treatment effect of secukinumab 150 mg s.c. regimen compared to placebo in Chinese population. |
| Randomization (strata, allocation ratio) | At BSL, all eligible participants will be randomized via Interacive Response Technology (IRT) in a 1:1 ratio to one of the treatment arms. At Week 16,all participants will be re-randomized in a 1:1 ratio to secukinumab 150 mg s.c. to enable to assess long- term efficacy and safety of secukinumab 150 mg s.c. regimen |
| Blinding | Double-blinding is used in this study to minimize bias in the evaluation of safety and efficacy assessment. Blinding is maintained beyond the primary endpoint, to ensure reliable efficacy and safety measures over time. |
| Duration of study periods | Primary endpoint of the trial is assessed at Week 16, allowing for comparisons of efficacy at a point in time which is same as global PsA Phase III trials. The treatment duration in the placebo group is kept a minimum. The participants in placebo arm will start receiving active treatment at Week 16. The total study duration, including 52 weeks of treatment plus the follow- up period, will allow for the assessment of long term safety and efficacy. |

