All adverse events must be treated appropriately. Treatment may include one or more of the following:

- No action taken (i.e. further observation only);
- Study treatment temporarily interrupted;
- Study drug(s) permanently discontinued;
- Concomitant medication given;
- Non-drug therapy given.
- 6. Its outcome (not recovered/not resolved; recovered/resolved; recovering/resolving, recovered/resolved with sequelae; fatal; or unknown)

Conditions that were already present at the time of informed consent should be recorded in medical history of the participant.

Adverse events (including lab abnormalities that constitute AEs) should be described using a diagnosis whenever possible, rather than individual underlying signs and symptoms.

Adverse event monitoring should be continued for at least 12 weeks following the last dose of study treatment.

Once an adverse event is detected, it must be followed until its resolution or until it is judged to be permanent (e.g. continuing at the end of the study), and assessment must be made at each visit (or more frequently, if necessary) of any changes in severity, the suspected relationship to the interventions required to treat it, and the outcome.

Information about adverse drug reactions for the investigational drug can be found in the Investigator's Brochure (IB).

Abnormal laboratory values or test results constitute adverse events only if they fulfill at least one of the following criteria:

- they induce clinical signs or symptoms
- they are considered clinically significant
- they require therapy

Clinically significant abnormal laboratory values or test results must be identified through a review of values outside of normal ranges/clinically notable ranges, significant changes from BSL or the previous visit, or values which are considered to be non-typical in participant with the underlying disease. Alert ranges for laboratory and other test abnormalities are included in Section 16.1.

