2.1.1.2 Study Day 1 and other study days

The first day of administration of randomized study treatment (first dose) is defined as Study Day 1 or Day 1.

All other study days will be labeled relative to Day 1. For event dates on or after Day 1, study day for a particular event date is calculated as [Date of event] – [Date of first dose] + 1, i.e., Day 2, Day 3, etc., will be one day, two days, etc., after Day 1, respectively. For the dates before Day 1, study day for an event date is calculated as [Date of event] – [Date of first dose], i.e., Day -1, Day -2, etc., will be one day, two days, etc., before Day 1, respectively. Duration of an event will be calculated as (Event end date – Event start date + 1).

The descriptor “Day 0” will not be used.

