2.7 Safety analyses

Summaries will be performed for the entire treatment period on the Safety Set.

Safety analysis will be performed on treatment received or actual treatment as described below:

The actual treatment or treatment received for summaries of safety data would differ to the treatment assigned at randomization only if a subject received the wrong treatment during the entire study.

For those subjects who received not the treatment assigned at randomization, i.e., who received erroneously the wrong treatment at least once, an additional AE listing will be prepared displaying which events occurred after the treatment errors.

Subjects who switch treatment during the study (e.g. from placebo to active treatment) will be counted to both groups using the appropriate start and stop exposure date.

The safety variables to be analyzed include Adverse events (AEs)/Serious Adverse Events (SAEs), clinical laboratory tests (hematology, chemistry and urinalysis), physical examination results, ECGs, vital signs and deaths. Safety variables are to be tabulated by descriptive statistics (n, mean, median, standard deviation, minimum, and maximum; or n and percent). No formal statistical testing is planned.

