2.7.1 Adverse events (AEs)

Treatment-emergent adverse events (i.e., events started after the first dose of study treatment or events present prior to the first dose of study treatment but increased in severity based on preferred term and on or before last dose + 84 days) will be summarized.

Adverse events will be summarized by presenting, for each treatment group, the number and percentage of participants having any AE, having an AE in each primary system organ class and having each individual AE (preferred term). Summaries will also be presented for AEs by severity and for study treatment related AEs. If a participant reported more than one adverse event with the same preferred term, the adverse event with the greatest severity will be presented. If a participant reported more than one adverse event within the same primary system organ class, the participant will be counted only once with the greatest severity at the system organ class level, where applicable. Serious adverse events will also be summarized.

These summaries may be presented separately by placebo controlled period and entire study.

As appropriate, the incidence of AEs will be presented per 100 patient years of exposure (exposure-adjusted incidence rates).

Separate summaries will be provided for death, serious adverse event, other significant adverse events leading to discontinuation and adverse events leading to dose adjustment (including study treatment discontinuation).

A graphical display of relative frequencies within system organ classes and relative risks, as appropriate, will be presented.

Adverse events will also be reported separately by Standardized MedDRA Query (SMQ) according to MedDRA. The MedDRA version used for reporting the study will be described in a footnote.

Treatment emergent and non-treatment emergent adverse events will be listed.

Algorithms for date imputations will be provided in Programming Datasets Specifications.

For serious adverse events (SAEs) occurred during screening a listing were prepared for all subjects screened including screening failures at the primary endpoint analysis.

The safety analysis that will be performed for treatment emergent AEs and on treatment labs and vital signs for each analysis period is described in Table 2-1.

The data in the period of Day 1 – Week 16 were presented at the primary endpoint analysis; the data in the period of Entire treatment will be presented at the Final Analysis.

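### Emergence and worsening of adverse events are judged only against the first dose of any study treatment, so separate placebo and secukinumab columns have no worsening rule for events that begin on placebo

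*Protocol*

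**What the plan says.** Both documents use the same definition. Protocol 12.5.2 counts "events started after the first dose of study treatment" and "events present prior to the first dose of study treatment but increased in severity based on preferred term", up to 84 days after the last dose. SAP 2.7.1 repeats it: "events started after the first dose of study treatment or events present prior to the first dose of study treatment but increased in severity".

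The reference dose is fixed at baseline. The protocol glossary says that study treatment "includes investigational drug(s), control(s) or background therapy", and SAP 2.1.1.2 states: "The first day of administration of randomized study treatment (first dose) is defined as Study Day 1 or Day 1". Nothing resets it at Week 16, although protocol 4.1 says: "The participants in placebo arm will start receiving active treatment at Week 16".

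SAP 2.1.1.1 makes treatment sequence the default grouping at the final analysis. For some safety summaries, with exposure-adjusted ones as the example, it allows separate columns: Placebo, Any AIN457 150 mg, a second secukinumab regimen that is redacted, and Any AIN457. SAP 2.4.1 divides a switcher's exposure between treatments, and SAP 2.7 says that switchers "will be counted to both groups using the appropriate start and stop exposure date". SAP Table 2-1 plans exposure-adjusted incidence over the entire treatment for AEs and SAEs, SMQs and risks.

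On data capture, protocol 10.1.1 follows each event until it resolves or is judged permanent, and "assessment must be made at each visit (or more frequently, if necessary) of any changes in severity". It does not say whether a worsening is a new record or an update of the existing one.

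**The concern.** A participant's time is split at the switch, but the test for emergence is not. Once person-time is divided between Placebo and Any AIN457, every event needs a matching numerator rule. For an event that begins on placebo, is ongoing at Week 16 and worsens after the first secukinumab dose, there is none.

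The two groups that feed Any AIN457 are then treated differently. In Group 1, worsening after the first secukinumab dose of something already present is emergent on secukinumab. In Group 2, the same sequence relative to the first secukinumab dose has no worsening route if the event began during the placebo period. The pooled column could therefore miss part of what happens on first exposure to secukinumab.

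**Working it through.** The documents state no figure for this point, so there is none to reproduce. The check is a comparison of the rules, followed by simple person-time arithmetic.

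**The rules applied to a condition present at the first secukinumab dose that worsens afterwards**

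- Group 1: present before Day 1, worse later. Emergent through the worsening limb and counted under secukinumab.
- Group 2, present before Day 1 and first worse after Week 16: also emergent through the worsening limb.
- Group 2, began on placebo and worse after Week 16: emergent only because it started after Day 1. The worsening limb does not apply, because the event was not present before the first placebo dose.

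**Where the third case can land**

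1. By-sequence table: once, under the Placebo – AIN457 sequence. No misattribution between columns arises.
2. Separate columns, one record, assigned by start date: under placebo only.
3. Separate columns, worsening entered as a new record dated after the switch: it starts after the first dose and can be counted under secukinumab.
4. Separate columns, one record overlapping both exposure intervals and counted in both: it appears under secukinumab too, but so would any ongoing placebo event that never worsened.

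Readings 2 to 4 give different tables, and neither document chooses between them.

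**What one participant is worth in an exposure-adjusted table**

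Inputs: 20 participants per arm (protocol 6.1.3), switch at Week 16, last planned dose at Week 48 (protocol Table 6-4), and exposure to last dose plus 84 days (SAP 2.4.1), which is Week 60. Assumptions: no dropout, and simple person-time without censoring at first event.

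- Placebo: 20 × 16 × 7 / 365.25 = 6.1 person-years.
- Secukinumab, Group 1: 20 × 60 = 1,200 weeks. Group 2: 20 × 44 = 880 weeks. Total: 2,080 × 7 / 365.25 = 39.9 person-years.
- One participant in the placebo numerator: 100 × 1 / 6.1 = about 16 per 100 person-years.
- One participant in the secukinumab numerator: 100 × 1 / 39.9 = about 2.5 per 100 person-years.

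The note to Table 2-1 places these rates at primary system organ class, or Level 1 for risks and SMQs. A participant therefore changes a rate only if they have no other qualifying event in that category and column.

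**The case against.** A reader might infer that such an event is always booked under placebo at its worst grade and never under secukinumab. The documents do not say so. SAP 2.7 speaks of exposure dates, not event start dates, and counting switchers in both groups can be read as covering overlapping events. One record per event is not stated either. Protocol 10.1.3 has progression of an SAE reported as follow-up to the original episode, which makes that reading plausible. However, SAP 2.7.1 also foresees consecutive records of the same term in its registry tables.

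A reader might also infer that no worsening can be counted during Group 2's secukinumab time. That is wrong: a condition that predates Day 1 and first worsens after Week 16 qualifies.

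Nor are these events invisible. Treatment-emergent and non-emergent events are all listed, by treatment sequence. The by-sequence tables have no placebo-only column to distort, the Day 1 to Week 16 comparison ends before the switch, and safety is descriptive with no formal testing.

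Inflation of placebo grades is also not established. Table 2-1 plans AEs by severity as crude incidence only, and the default grouping is by sequence, so it would arise only if that table were split. The greatest-severity rule sits in a paragraph about summaries for each treatment group, so applying it within a column is the natural reading.

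All of this narrows the point. It does not supply an attribution rule for the separate columns. The by-sequence tables do not supply one either: they merge both periods, and SAP 2.7.1 names only the placebo-controlled period and the entire study as separate summaries.

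**Conclusion.** The concern holds for entire-study safety summaries with separate Placebo and Any AIN457 columns. There, the single reference dose leaves events that begin on placebo and worsen after the switch without a worsening route to secukinumab, while Any AIN457 pools Group 1 and Group 2 under unequal definitions.

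That such events are counted under placebo alone depends on two unstated conditions: one record per event, and assignment by start date. Only under those conditions does the omission lower the secukinumab rate. An event that began on placebo belongs in the placebo column in any case, so what is lost is its additional appearance under secukinumab.

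At most the 20 planned placebo participants are concerned, and the number of events cannot be derived. Each affected participant is worth about 2.5 per 100 person-years in the secukinumab column and about 16 in the placebo column, under the full follow-up assumed above. The change should be made: it replaces a stated rule that does not fit the planned columns, and this SAP is the one written for the final database lock.

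**What to change.** In SAP 2.7.1, for any table with separate placebo and secukinumab columns:

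- Define an adverse event as emergent on a treatment if it starts after the first dose of that treatment, or was present at that dose and increased in severity afterwards. For Any AIN457, the reference is the first dose of any secukinumab regimen.
- Apply the greatest-severity rule within participant and treatment, using the grade reached in that exposure interval where the data record it.
- Where only one grade per event is held, list the events that straddle the switch and flag them in a footnote. Do not ask sites to re-enter records: all participants have passed Week 16, so that would mean retrospective querying.

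The cost is SAP wording and some extra programming. A few events will appear in both columns, which a footnote should explain. Tables by treatment sequence and the Week 16 analysis need no change.
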